### **Screening Visit: Consent & Eligibility**

- Meet RA and study team
- Explain study and sign informed consent
- Sign medical release of information form
- Conduct rapid HIV test
- Review and/or obtain lab work to confirm eligibility

#### **If eligible:**

- Order 90-day supply of digital PrEP

#### **If ineligible:**

- Refer back to PCP for treatment / continued medical care

### **Study Visit 1: DigiPrEP Setup**

- Self-report questionnaire
- Technology training
- Dispense 30 days of PrEP (Truvada digital pill)

- DigiPrEP interface text messages on days 1, 2, 5, 7 to ensure DigiPrEP is working
- DigiPrEP interface text messages on days 23, 25, 29 to remind participants of Study Visit 2

### **Study Visit 2: Day 30 (-7 days)**

- Review DigiPrEP data
- Blood draw for adherence
- Refill 30 days of PrEP (Truvada digital pill)

- DigiPrEP interface text messages on days 53, 55, 59 to remind participants of Study Visit 3

### **Study Visit 3: Day 60 (-7 days)**

- Review DigiPrEP data, pill counts
- Refill 30 days of PrEP (Truvada digital pill)

- DigiPrEP interface text messages on days 83, 85, 89 to remind participants of Study Visit 4

### **Study Visit 4: Day 90 (-7 days)**

- Review DigiPrEP data, pill counts, return equipment
- Blood draw for adherence

## VI. Biostatistical Analysis

Aim 1: We will conduct qualitative analysis on individual interviews in aim 1 to elucidate themes of technology acceptance, design, and optimal timing and delivery of messaging.

Aim 2: We will calculate descriptive statistics regarding the degree of adherence collected from the digital pill. We will also calculate the accuracy of the digital pill in comparison to pill counts and validate ingestion data compared to dried blood spot data. Because this is a pilot, proof-of-concept study, we will not be powered to determine the degree of adherence the use of a digital pill alone confers upon study participants.

## VII. Risks and Discomforts

We anticipate the major risks due to DigiPrEP are the potential for exposure to metal components in the digital pill, and retention of the radiofrequency emitter portion of the digital pill. Major psychological discomforts could occur during study interviews when participants are asked about their adherence patterns.

**Exposure to Metal Components in Digital Pill:** The Digital Pill is manufactured from the same basic components as other ingestible medical devices. The radiofrequency tags contain minimal amounts of silver, zinc and magnesium that are significantly less than the recommended daily intake of these metals. In order to prevent absorption of these metals, the radiofrequency tag is coated with an epoxy and ethyl cellulose coating in a technique that is used for other ingestible medical devices. Extensive experience in the use of ingestible small bowel endoscopy cameras has not reported adverse events related to the exposure of electronic components.

**Digital Pill Radiofrequency Emitter Retention:** Study participants may experience retention of the radiofrequency emitting portion of the digital pill. A study assessing the efficacy of the capsule portion of DigiPrEP among healthy volunteers documented 560 successful ingestion events without any adverse effects. [name] has completed a pilot study that recorded 96 ingestions with the digital pill containing oxycodone without any adverse events. Additional pilot data from Novartis of over 100 participants who ingested radiofrequency tagged gelatin capsules revealed no reports of sensor retention (Personal communication from [name], Novartis). An additional investigation to determine the safety of digital pills demonstrated no retention of any of the components of the digital pill by abdominal imaging. The best comparison to the digital pill are capsule endoscopy pills which are over twice the size of digital pills. Over a decade of experience of capsule endoscopy has revealed a capsule retention rate of less than 2%. In the case of a retained endoscopy pill, patients were mostly asymptomatic, and treatment consisted only of oral fluid administration. Patients who elected to have the capsule removed successfully underwent elective partial small bowel resection with pathologic findings including mild bowel stricture or intimal ulceration from capsule retention. Complication rates among patients with Crohn's disease, bowel neoplasm, radiation enteritis, or stricture were higher. In high-risk patients, standard therapy for retained endoscopy pills included aggressive oral hydration with successful removal of the retained pill. We believe that the risk of retention of a DigiPrEP capsule will be less than that of a capsule endoscopy pill given the smaller dimensions of the digital pill. Unlike a capsule endoscopy pill, DigiPrEP is dissolvable with only the radiofrequency emitting portion of the capsule passing through the gastrointestinal tract. In order to minimize the risk of DigiPrEP capsule retention, we plan to exclude patients with underlying bowel disease or surgical intervention to the bowel.

Psychological discomfort of disclosing adherence patterns: Participants may experience psychological discomfort in disclosing and learning of their adherence data during study visits. As their Fenway Health PCP may be given participant's adherence data, participants may also experience the psychological discomfort knowing that their PCP knows about their adherence to PrEP during the study period.

## VIII. Potential Benefits

Participants may indirectly benefit from participation in the study by improving their adherence to PrEP. Interacting and using DigiPrEP may confer some increased adherence among study participants.

## **IX. Data Monitoring and Quality Assurance**

We will review and monitor data from DigiPrEP for each study participant. At each study visit, participants will undergo pill counts to correlate adherence data from DigiPrEP, and calculate the accuracy of the digital pill to measure PrEP adherence. Any discrepancies between the digital pill and pill counts will be addressed in real time at each study visit with the participant. For each participant, we will also review signaling from the digital pill to the Reader with our industry collaborator (eTectRx) to ensure there are no errors in data transmission contribution to missed adherence events. If errors occur as a result of data transmission, we will annotate this on the ingestion data.

The study investigators will conduct QA to review data after half of the patients (N=7) of Aim 2/3 are enrolled to ensure that data is accurate and no errors have been made.

The principal investigator ([name]) will be responsible for monitoring adverse events during the study, but Drs. [name] and [name] will assume this responsibility in the event that [name] is unavailable. The role of the responsible person is 1) to identify the concern, 2) develop an appropriate response that involves consultation whenever possible to alleviate or minimize any adverse event, and 3) to ensure that the adverse event is reported in a timely manner to the responsible authority.

Participants will be monitored for occurrence of events defined as any undesirable experience or unanticipated benefit. Events may occur during recruitment, technology deployment, and qualitative interviewing. For example, a participant may become distressed when asked questions about substance abuse and its impact on PrEP adherence. Based upon previous research couched in technology among hidden populations, we anticipate that these effects will be minimal. The principal investigator will assess whether an undesirable experience occurred (adverse event) and will record details of all adverse events (death, life threatening illness, new serious or permanent disability) that occur. Should such an event occur, the principal investigator will report the event within 24 hours to the Fenway Institute IRB.

The adverse event case report form will include a description of all undesirable experiences, required interventions, and an assessment of the subject after the event if possible. An estimate of the extent of injury, and prevention strategies will be reported. The principal investigator will classify the relationship of the study protocol to the event as follows:

- **Not related:** The event is clearly related to factors such as the subject’s clinical state, not with the study protocol.
- **Remote:** The event was most likely related to factors such as the subject’s clinical state, not with the study protocol.
- **Possible:** The event follows a reasonable temporal sequence associated with participating in the study and/or is consistent with events related to responding to queries about stress/drug craving but is possibly related to factors such as the subject’s clinical state.
- **Probable:** The event follows a reasonable temporal sequence associated with participating in the study and/or is consistent with events related to responding to DigiPrEP or digital pills and cannot be reasonably explained by factors such as the subject’s clinical state.

The severity of an adverse event in both groups is defined as a qualitative assessment of the degree or intensity of an adverse event as determined by the principal investigator as follows:

- **Mild:** No impact (in anyway) on the subjects.
- **Moderate:** Impacts on the subject but is not life-threatening or incapacitating.
- **Severe:** Fatal, life threatening, permanently disabling; severely incapacitating; requires/prolongs inpatient hospitalization.

All adverse events will simultaneously be reported to the NIH project officer. The report will summarize the facts of the case, including the date and a description of the subject; whether the event is related to the study's protocols; the steps that have been taken to address the issue; whether the event provides emerging knowledge about the risks of the study that should be conveyed to respondents; and whether the consent form should be revised.

### **Data Safety Monitoring Board**

[name], will select three external investigators with expertise in PrEP, substance use disorder, technology security and behavioral interventions to participate on a data safety monitoring board (DSMB) for aim 2 (pilot randomized controlled trial) of the research plan. The DSMB will convene annually during aim 2 of the research plan. Additionally, the DSMB will meet when N=10 study participants are enrolled in aim 2. They will review the data, and any potential study related adverse events prior to approving the continuation of recruitment. The responsibilities of the DSMB will include:

- Reviewing the research protocol, consent form, and plans for DSMB.
- Evaluating the progress of the pilot randomized controlled trial: recruitment, retention, data quality, site performance, adverse events.
- Protection of participant safety
- Making recommendations to [name] and the Fenway Institute IRB regarding continuation, termination or modification of the study depending on benefits or adverse events.
- Ensuring the confidentiality of study data.
- Reviewing adverse events.
- Providing annual written reports to [name], and Gilead Sciences (study sponsor) required regarding safety concerns, continuation or modification of the research plan.

**Data Safety.** The protection of data for this study includes the following: 1) Data are collected through a HIPAA compliant web server hosted by eTectRx, then securely relayed to a cloud-based program (NOMI) that drives smart interventions in DigiPrEP. The cloud-based database is hosted behind the secure firewall through eTectRx, and accessed through Fenway Health computers. 2) Study participants are identified by a unique numeric identification; their protected health information (PHI) is never linked to ingestion data captured by eTectRx, or the cloud-based program. 3) Study participant PHI is collected and stored on a secure Microsoft Excel worksheet which will be created on a secure, password protected desktop computer located at TFI where only [name], his study mentors and a trained research assistant (RA) will have access. 4) All data (ingestion data on the cloud-based database and PHI) is stripped of all identifying information by [name] prior to transmission to collaborators at BWH, MGH, BIDMC and Children's hospital. We will also share deidentified data with our sponsor, Gilead Sciences. 5) Deidentified ingestion data as well as demographic data will be securely stored on the TFI server; we will access this data for later investigations under a separate IRB protocol. 6) At study completion, the link between the identifying information and their data is destroyed, as is contact information. Two sets of the cleaned data set will be maintained—one working copy at Brigham and Women's Hospital, and one at the Fenway Institute. This approach ensures that the data survives a failure of one storage location. 6) Finally, all study staff have completed the CITI Course in the Protection of Human Subjects online training in research ethics and good clinical practice to ensure that all staff are compliant with confidentiality training.

**Data Tracking:** Data will be automatically logged into the web interface hosted by eTectRx with a date/time stamp to ensure accurate record keeping of all data and linking to the results. All data will be securely accessed at Fenway Health.

**Data Entry Process:** Protected health information, including study participant demographics, substance use disorder history, and HIV risk factors will be collected by [name] and the research assistant and entered into REDCap, a secure web application being used for data storage and management. A separate spreadsheet of

study participant contact information and a technology log including participant mobile phone number, electronic mail (email) address, identifiers of the Receiver, study smartphone and a log of dispensed digital pills will also be maintained by [name] and the RA. All logs will be stored behind TFI firewall and password protected. [name] will also maintain a second copy of the logs as a backup in his secure office behind the BWH firewall. Data loaded onto the interface cannot be edited. Each variable with missing data (such as an interruption between smartphone and sensor) will be identified and a placeholder (“<<-99>>”) is entered to connote a missing value. Data from the digital pill is recorded on the eTectRx interface and automatically transferred via a HIPAA-compliant secure link to the adherence interface (NOMI). Ingestion data may potentially require editing if there are transmission failures, errors from the reader device, or manually recorded data from study participants. All of these potential edits will be identified by eTectRx in collaboration with the study team. Edits to data will be agreed upon by both parties and approved by the PI. An audit trail of all potential edits will be maintained, one copy at eTectRx and one copy at TFI. We will additionally comply with Fenway regulations regarding reporting of adverse events and ensuring data quality. Landmark Associates Inc, an external company, will be contracted to transcribed audio-taped interviews.

**Data storage:** Raw ingestion data, transcripts from this study and self-report questionnaires will not be made publicly available. Deidentified data may be shared with Gilead Sciences who is funding the study, as well as industry collaborators eTectRx and NOMI. For future investigations that use deidentified participant data, we will submit IRB protocols detailing the use of this data. Partners Health Dropbox is being used for file storage in the study.

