**Aim 2 – Study Visit 2:** We will contact participants on days 23, 25, and 29 to remind participants of their Study Visit 2 appointment. During this study visit, participants will have blood drawn via phlebotomy and placed on a blood spot card in order to assess PrEP adherence. De-identified specimens will be banked for future use in drug abuse screening. We will review digital pill adherence data with participants in Nomi and conduct a pill count to validate adherence data from the digital pill and Reader. We will review discordant counts, periods of Reader activity that suggest no use of the Reader device, and digital pill use with the participant. We will additionally review any potential nonadherent events detected by the digital pill with participants using timeline followback to gauge potential reasons for nonadherence. We will view the adherence interface with study participants and discuss events surrounding potential nonadherence events. We will record user responses to

each of these timeline followback events. We will also dispense an additional 30-day supply of digital pills to participants. We will schedule participants for Study Visit 3 prior to discharge, which will occur a maximum of 30 days (i.e., 23-30 days) after Study Visit 2. Participants will be reminded that we will pass their adherence data along to their PCP; participants will have the option of opting out of this mechanism at each study visit. At the end of Study Visit 2, the participant will be remunerated via a \$25 check.

**Aim 2 – Study Visit 3:** We will contact participants on days 53, 55, and 59 to remind them of their Study Visit 3 appointment. During this visit, we will review adherence data from the digital pill in Nomi, conduct pill counts with participants, address discordant counts and review reader activity with the participants and address any nonadherence events potentially linked to sexual activity or substance use. The participant will receive a final 30 day refill of digital pills and will be remunerated via a \$50 check.

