DigiPrEP Statistical Analysis Plan

Official title: Feasibility and Acceptability of Digital Pills to Monitor PrEP Adherence in MSM With Substance Use

NCT number: NCT03842436

Document date: September 03, 2021

DigiPrEP Statistical Analysis Plan

Sociodemographics.

Descriptive statistics were calculated for selected variables.

Digital pill system (DPS) performance and engagement metrics.

To analyze the performance of the DPS, the ground truth of PrEP ingestion events were defined as the pill counts obtained each month (i.e., the number of unused pills returned, subtracted from the number of pills previously dispensed). The number of DPS-recorded ingestions – which included the number of both Reader-detected and manually-reported ingestions – was compared with the aggregate pill count at each monthly timepoint; this was defined as the overall performance metric for the DPS. The Reader-detected ingestions count was used to reflect the number of times the DPS was operated correctly. Successful DPS operation was defined as ingestion of a digital pill, proper use of the wearable Reader, and confirmation of the ingestion on both the Reader and the app.

Reader-detected ingestions and manually-reported ingestions that co-occurred within 30 minutes were identified and reconciled; these events likely represented episodes in which a digital pill was ingested, and the ingestion was detected by the Reader, but the participant elected to manually record the ingestion in-app because the Reader was not correctly paired to the smartphone or was delayed in detecting the ingestion. Additionally, several ingestions were manually reported due to a known programming error in the app early in the study. As such, two participants were instructed to manually log all ingestions until an app update was made available; ingestion data for these two individuals were downloaded from their Readers at the end of the study period, and all Reader-detected ingestions were reconciled with manually-reported ingestions.

Participant engagement with the DPS was measured by calculating the total number of DPS-recorded ingestions and comparing the number of monthly DPS-recorded ingestions across each month of the study period.

TFV-DP in DBS.

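### Digital pill records can be edited without blinding to the pill count they are then judged against, and the SAP does not say whether edited or unedited records enter the performance metric

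*Protocol*

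**What the plan says.** **Editing rule.** The Data Entry Process paragraph of Protocol Section IX states: "Ingestion data may potentially require editing if there are transmission failures, errors from the reader device, or manually recorded data from study participants". On who does this, it says: "All of these potential edits will be identified by eTectRx in collaboration with the study team". On authority, it says: "Edits to data will be agreed upon by both parties and approved by the PI". An audit trail is kept in two copies, one at eTectRx and one at the study site. A pill-count mismatch is not a listed ground for editing, and no timing is given.

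**Other treatments of the same problem.** The same paragraph also says: "Data loaded onto the interface cannot be edited". It assigns a -99 placeholder to missing values, with a break between phone and sensor as its example. The opening of Section IX says that transmission errors are annotated on the ingestion data.

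**Knowledge of the count.** For Study Visit 2, Protocol Section V says: "We will review digital pill adherence data with participants in Nomi and conduct a pill count to validate adherence data". Discordant counts are then reviewed with the participant. Section IX adds: "Any discrepancies between the digital pill and pill counts will be addressed in real time at each study visit with the participant". It also has signalling reviewed with eTectRx for each participant "to ensure there are no errors in data transmission contribution to missed adherence events".

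**Metric.** The SAP section on system performance takes the monthly pill count as the true number of ingestions. It compares Reader-detected plus manually reported ingestions with that count and says "this was defined as the overall performance metric for the DPS". Reader and manual records within 30 minutes of each other are reconciled. For two participants affected by an app error, Reader data were downloaded at the end of the study and reconciled with their manual reports.

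**The concern.** A measure of agreement informs only if the record under test is fixed without knowledge of the reference. Here one of the two editing parties holds the reference, and it works with the company whose system is being measured. If gaps are looked for, or restored, because the pill count shows that they exist, part of the agreement is created by the review.

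A lost transmission or a Reader fault is also something that a reader of the performance result would want to see counted. Once edited in, it disappears from the shortfall. The result could then overstate what the system captures in use where nobody reconciles the record. The SAP leaves the matter open because it does not name the version of the record that it analyses.

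**Working it through.** The documents give no accuracy target, accuracy result or number of edits, so there is no figure of the plan's own to reproduce. The check has four steps.

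**1. Are the record and its reference kept apart?**

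- Who may change the record: eTectRx and the study team, with PI approval (Protocol IX, Data Entry Process).
- Who knows the count: the study team, at Visits 2 to 4 (Protocol V and IX).
- What the count is used for: the reference for the overall performance metric (SAP).
- Blinding of editors, a lock before the count, or a named version for analysis: none found in either document.

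**2. What does one edit do?** Let D be recorded ingestions, P the pill count, a the events added and r the events removed. The ratio is A = D/P, and editing changes it by (a − r)/P.

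One participant-month, assumed P = 25 and D = 20:

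- as captured: 20/25 = 80%
- one event added: 21/25 = 84%
- three added: 23/25 = 92%
- five added: 25/25 = 100%

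Whole study: at most 15 × 90 = 1350 pills are supplied. With an assumed P = 1200, 60 events are 60/1200 = 5.0 points:

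| D before edits | 60 removed | no edits | 60 added |
|---|---|---|---|
| 1000 | 78.3% | 83.3% | 88.3% |
| 1200 | 95.0% | 100.0% | 105.0% |
| 1260 | 100.0% | 105.0% | 110.0% |

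**3. Which direction?** Agreement is best at 100%. Additions improve it only while D is below P, and they can overshoot. Removals worsen it when D is at or below P and improve it when D is above P. The signal review looks for causes of missed events, which points to additions. The 30-minute rule, read here as counting a matched pair once, points to removals.

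**4. Does knowing the count matter beyond the editing itself?** All rates here are assumed: 30 pills a month, 90% taken, 3% of untaken pills lost, 80% of taken pills detected, duplicate manual entries for 8% of detected events, and 25% of missed events restorable. Expected values per participant-month:

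- P = 27 + 0.03 × 3 = 27.09
- detected = 0.80 × 27 = 21.6; duplicates = 0.08 × 21.6 = 1.728; missed = 27 − 21.6 = 5.4
- captured, duplicates left in: 23.328/27.09 = 86.1%
- captured, duplicates removed: 21.6/27.09 = 79.7%
- duplicates removed and a quarter of missed events restored, blind to the count: (21.6 + 1.35)/27.09 = 84.7%

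A simulation of 15 × 3 = 45 participant-months (4000 runs) gave the same three ratios. Removing duplicates alone worsened agreement in every run. When edits were made only where they brought the record closer to the count, the ratio was 90.5% and the mean absolute monthly difference was 2.59 pills, against 84.7% and 4.14 pills for blinded editing. The gap is 90.5 − 84.7 = 5.8 points.

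That gap needs care. It arises largely because selective editing leaves duplicates in place when the record is short (1.728/27.09 = 6.4 points). If the SAP's 30-minute rule removes them regardless, and the same quarter of missed events is restored, selective and blinded editing both give 84.7%, because restored events cannot exceed the shortfall. Knowing the count then matters only if it changes how many gaps are restored. Each further quarter of missed events adds 1.35/27.09 = 5.0 points. The ratio runs from 79.7% with none restored to 27/27.09 = 99.7% with all restored.

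**The case against.** The strongest case on the other side has five parts.

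- **The grounds are technical and the process is controlled.** Two parties must agree, the PI approves, and a trail is kept. This stands as a safeguard on accountability. It is not blinding, and no analysis of the trail is planned.
- **Recovering stored data is not fitting the record to the count.** Protocol Section I says that the Reader stores ingestion data as well as relaying it. An ingestion that the Reader logged and the app missed is real evidence. This stands, and is why late downloads deserve their own line and should not be dropped.
- **Section IX annotates transmission errors and uses a placeholder for missing values.** This also stands: the documents do not show that gaps are routinely turned into ingestions. But these statements conflict with the editing rule, and the SAP does not say which one feeds the numerator.
- **There are other measures.** The SAP uses the Reader-detected count for correct operation and compares the records with drug levels in dried blood spots, a reference that does not depend on pill counts. Neither replaces the overall metric, Reader errors are themselves a ground for editing, and the blood-spot analysis yields correlations and no capture rate.
- **The visit order proves little.** Review of the record is listed before the pill count, but the text fixes no sequence. Participants can see their own data in the app anyway, so reordering the steps would not blind them.

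A reader might infer that agreement can only rise. Duplicate reconciliation and overshoot both contradict that. A reader might also infer that edits are made after the count and because of it. The documents permit this but do not state it: addressing a discrepancy with a participant is not the same as editing the record. Nor do they show that pill counts guided the reconciliation for the two app-error participants.

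**Conclusion.** The point holds as a gap in safeguards. The record may be changed by people who know the reference, and the analysed version is not named, so independence of the overall performance metric is not assured. Confidence in this is high, because it rests on the text alone.

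That the bias is more likely upward is a judgement of moderate confidence. It rests on the stated aim of the signal review and on the assumption that recorded ingestions fall short of the pill count. The size is unknown. The 4 points per event in a 25-pill month and the 5 points per 60 events in 1200 are arithmetic on assumed counts, and the simulated ratios rest on assumed rates. If there were few edits, or if recoveries and duplicate removals offset each other, the effect could be negligible. The plan as written gives a reader no means of telling. The change is worth making, but this is not evidence that the result is wrong.

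**What to change.** 1. From the audit trail, compute the overall performance metric on records as captured: Reader-detected plus manual ingestions, with only the SAP's 30-minute de-duplication applied. Compute it again on edited records and show both.
2. Show the end-of-study Reader downloads for the two app-error participants as a separate line.
3. Report the number of edits, the reason and direction of each, and whether it came before or after the relevant pill count was known.
4. For any remaining or future visits, save a timestamped export before the pill count is compared, and make edits under fixed rules by people blind to the count.
5. Reconcile the four statements in Protocol Section IX (no editing after loading, the -99 placeholder, editing by agreement, and annotation), and state in the SAP which treatment feeds the numerator.

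The cost is a modest amount of extra analysis, one export per visit where visits remain, and a possibly lower reported figure. The SAP is dated September 2021 and written in the past tense, so item 4 cannot help data already collected; items 1 to 3 can. They assume that the trail holds enough detail to restore the captured values. If it does not, report how many records are affected.
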